9.2. Use of Medications

All medications taken by or administered to study participants in all 4 cohorts (LEAP Participants, Older Siblings, Younger Siblings, and Parents) beginning 30 days before enrollment and continuing throughout study participation will be collected. All medications used will be coded according to the WHO drug dictionary. The number and percentage of participants receiving prior and concomitant medications/therapies will be presented by LEAP Trio cohort and overall and by medication class.

10. OTHER ANALYSES

10.1. Lung Function

The lung function tests will be used to assess lung function in relation to asthma symptoms, asthma medication use and aeroallergen sensitization at V144 in LEAP Participants and Siblings. The lung function tests include forced expiratory volume (FEV1), forced expiratory volume to forced vital capacity ratio (FEV1/FVC) and peak flow.

10.1.1. LEAP Participants

FEV1 measurements collected at V144 for the LEAP Participants in the ITT population will be compared between LEAP Consumers and LEAP Avoiders using a linear regression model with covariates for asthma symptoms, asthma medication use and aeroallergen. The distribution of FEV1 will be examined to determine if a transformation should be applied to the measurements.

The same statistical methodology will be repeated to analyze FEV1/FVC and peak flow.

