# 2.2 SECONDARY OBJECTIVES

## **LEAP Participants**

- To assess the effect of peanut consumption or avoidance in an at-risk study population (former LEAP participants) on additional allergic disease outcomes such as: a) allergic sensitization to select ingested allergens, b) allergic sensitization to select aeroallergens, c) reported type 1 immediate-onset food allergy, d) seasonal and perennial rhino-conjunctivitis, e) oral allergy syndrome, and f) asthma.
- 2. To assess the long-term safety of the LEAP intervention as determined by the frequency and severity of peanut-related adverse events as well as by nutritional evaluations.
- 3. To assess eczema severity by clinical assessment of SCORAD.
- 4. To define the long-term immunological impact of the intervention using cellular and humoral assessments of immune response related to the development of allergy or tolerance to specific allergens.

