## Figure 1. LEAP Screening, Participant, Sibling, and Parent Cohorts

The number of siblings in the Ad Lib section are based on findings in a survey regarding siblings of LEAP participants. These numbers represent an estimate of the total participants expected to enroll.

Participants in the current study derive from participants in previous LEAP trials and their families. The LEAP Screening Cohort has been described. The LEAP study enrolled 640 participants, of whom 556 were also studied in the LEAP-On follow up study. All participants who enrolled in LEAP, including those who were not part of the intent-to-treat (ITT) population, are eligible to enroll in this study. Parents and siblings of LEAP participants who meet other eligibility criteria described in sections 4.2 and 4.3 are eligible to enroll.

We reviewed the ages and dates of enrollment of participants in the LEAP trial. The times of enrollment and participation are shown in Figure 2. We assume the trial opens for enrollment in March 1, 2018. The last day for enrollment is August 31, 2022. The study was extended to accommodate for slowed enrollment due to the COVID-19 pandemic. As a result of the study extension, participants are predicted to be older than originally planned. This difference is not likely to significantly alter the study outcomes, as allergic status is unlikely to change during this time interval. These parameters allow us to describe expected ages at enrollment of LEAP participants in the current study.

Participant A, and similar participants who were relatively old at enrollment and enrolled relatively early in LEAP, could be as old as [10.9 months + (August 31, 2022 - February 2, 2007)] = 332 + 5689 days or 16.5 years.

For participant E, and similar participants who were relatively young at enrollment and enrolled relatively late in LEAP, the minimum age for eligibility applies (section 4.1.1). At the time of trial opening they would be as young as [4.5 months + (March 1, 2018 - March 20, 2009)] = 137 + 2844 days or 9.3 years. The minimum age of 9.5 years for eligibility means such participants could therefore be eligible for enrollment 0.2 years after March 1, 2018, or in May 2018 or after.

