## 6.3 GENERAL ASSESSMENTS

## 6.3.1 Non-dietary Assessments

The following general assessments will be performed:

- Informed consent: Informed consent will be obtained before any study procedures are performed. For children younger than 16, assent will also be obtained.
- Eligibility criteria.
- Medical history.
- Physical examination: Temperature, pulse, respiratory rate, weight and height will be completed for LEAP participants and siblings <18 years of age. Skin fold thickness and waist circumference measurements will only be taken for LEAP participants.
- Urine pregnancy test on all post-menarcheal participants prior to undergoing an incremental oral food challenge.
- Concomitant medications: All concomitant medications will be recorded on the CRFs.
- Eczema: SCORAD: Both subjective and objective eczema severity criteria will be recorded. The modified SCORAD evaluation alone will be used for all remaining eczema evaluations.
- TEWL: this is a measure of water loss from skin and will be recorded for LEAP participants and siblings.
- Bed dust collection: All families will be sent a vacuum pack with an information sheet, consent forms and instructions on how to collect a dust sample from bed-sheets.
- Rhinoconjunctivitis and Oral Allergy Syndrome (OAS) evaluation: Symptoms in accordance with the study definitions for seasonal and perennial rhinoconjunctivitis and OAS will be recorded.
- Asthma: Symptoms in accordance with the study definition for asthma will be recorded and spirometry measurements taken for LEAP participants and siblings.
- Food reaction history: A history will be taken to determine if the participant has had any clinically significant food-induced, immediate-onset allergic reactions.

- Food Allergy History Questionnaire: A questionnaire relating to the consumption of common food allergens (including tree nuts and sesame), foods that commonly cause OAS symptoms, and any other foods causing reactions indicative of immediate onset food allergy or OAS will be completed for all participants.
- Adverse events: Participants will be assessed for adverse events. Adverse events will be recorded as described in section 8.

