8.3.7.1. LEAP Participants

The prevalence of asthma in the LEAP Participants in the ITT population will be compared between LEAP Consumers and LEAP Avoiders using a two-tailed, chi-squared test at the 0.05 level of significance.

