10.1.2. LEAP Siblings

FEV1 measurements collected at V144 for the LEAP Siblings in the ITT population will be compared between LEAP Consumers and LEAP Avoiders using a linear mixed effects model with a random family effect included to account for the clustering of siblings within family units and the analysis of multiple siblings. Covariates for asthma symptoms, asthma medication use and aeroallergen sensitization will be added to the model. The distribution of FEV1 will be examined to determine if a transformation should be applied to the measurements. Older Siblings and Younger Siblings will be analyzed separately.

The same statistical methodology will be repeated to analyze FEV1/FVC and peak flow.

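### The only planned arm comparison of lung function conditions on Visit 144 asthma symptoms, asthma medication and aeroallergen sensitisation and omits age, sex and height, so it may miss part of the total effect and loses precision.

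*SAP*

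**What the plan says.** SAP 10.1 gives the purpose of the lung function tests: to "assess lung function in relation to asthma symptoms, asthma medication use and aeroallergen sensitization at V144". SAP 10.1.1 then writes the analysis as a comparison of arms: "FEV1 measurements collected at V144 for the LEAP Participants in the ITT population will be compared between LEAP Consumers and LEAP Avoiders", by linear regression "with covariates for asthma symptoms, asthma medication use and aeroallergen", repeated for FEV1/FVC and peak flow. The word after aeroallergen is missing there, but 10.1 and 10.1.2 show that sensitisation is meant. For siblings, SAP 10.1.2 uses a mixed model with a random family effect and states: "Covariates for asthma symptoms, asthma medication use and aeroallergen sensitization will be added to the model".

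Section 10.1 contains no arm comparison without these covariates. Age, sex and height are in neither model. Neither document mentions percent-predicted values or z-scores; the only transformation considered depends on the distribution of FEV1.

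The covariates also appear as outcomes. SAP 8.3.7.1 states: "The prevalence of asthma in the LEAP Participants in the ITT population will be compared between LEAP Consumers and LEAP Avoiders". Protocol 2.2 lists, among the participants' secondary objectives, "b) allergic sensitization to select aeroallergens".

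On age, Protocol 4.1.1 sets a minimum of 9.5 years. The text under Protocol Figure 1 says that a participant who joined LEAP early and relatively old "could be as old as" 16.5 years. Protocol 4.2 sets no age limit for siblings. On body size, Protocol 6.3.1 says that "weight and height will be completed for LEAP participants and siblings" under 18 years of age.

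**The concern.** There are two separate problems.

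First, a comparison of randomised arms that holds later variables fixed does not estimate the total effect of the intervention if the intervention alters those variables. Protocol 1.2 says the study will examine whether the benefit reaches other atopic disease, so the plan treats an arm effect on asthma and sensitisation as an open question. It then fixes both when it compares lung function.

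Second, raw FEV1 and peak flow in growing children depend heavily on age, sex and body size. Leaving these out puts that variation in the error term.

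Secondary endpoint 5 names lung function testing, yet the asthma definition (Protocol 3.3.4, SAP 8.3.7) uses no spirometry. SAP 10.1 is therefore the only planned analysis of the spirometry data. A null result from it could be read as no effect of the intervention on lung function, a question that the model does not answer.

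**Working it through.** **1. Role of the covariates in LEAP participants**

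| Covariate in SAP 10.1.1 | Where the plan treats it as an outcome |
|---|---|
| Asthma symptoms | First limb of the asthma definition; asthma compared by arm in SAP 8.3.7.1 |
| Asthma medication use | Part of the second limb of the same definition |
| Aeroallergen sensitisation | Protocol 2.2, objective 1; skin tests and IgE compared by arm in SAP 8.3.3.1 and 8.3.4.1 |

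All are measured at the same visit as the outcome and after randomisation in infancy.

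**2. What conditioning can remove**

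The documents give no effect sizes, so these are assumptions: FEV1 is 0.5 SD lower with asthma, and the arm acts on FEV1 only through asthma. The total effect is the difference in asthma prevalence times 0.5 SD. The adjusted results come from a large-sample regression simulation (2,000,000 records per scenario). Its last column adds an unmeasured cause shared by asthma and FEV1.

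| Asthma, avoiders vs consumers | Total effect | Adjusted for asthma | Adjusted, with shared cause |
|---|---|---|---|
| 15% vs 15% | 0 | 0 | 0 |
| 20% vs 15% | 0.05 × 0.5 = +0.025 SD | 0.000 | −0.023 SD |
| 25% vs 15% | 0.10 × 0.5 = +0.050 SD | 0.000 | −0.045 SD |

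The part that acts through asthma disappears, and the sign can reverse. If the arm does not change asthma, nothing is lost.

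**3. Age range**

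The protocol's upper figure reproduces: (332 + 5689) / 365.25 = 6021 / 365.25 = 16.48 years, stated as 16.5. The lower end is the eligibility minimum of 9.5 years.

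**4. Precision lost by omitting age, sex and height**

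Let R² be the share of variance that these three explain; the documents give no value. Against a model with no other covariates, the standard error (SE) is inflated by 1/√(1 − R²). For illustration, take 80% enrolment of the 319 consumers and 311 avoiders in Protocol 9.3: 0.8 × 319 ≈ 255 and 0.8 × 311 ≈ 249. The difference detectable with 80% power at two-sided 0.05 is (1.960 + 0.842) × √[(1 − R²)(1/255 + 1/249)] in raw SD units. With the three variables omitted this is 2.802 × 0.0891 = 0.25 SD.

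| Assumed R² | SE inflation from omission | Detectable difference if included |
|---|---|---|
| 0.2 | 1.12 | 0.22 SD |
| 0.4 | 1.29 | 0.19 SD |
| 0.6 | 1.58 | 0.16 SD |
| 0.8 | 2.24 | 0.11 SD |

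Spirometry is not done at home or telephone visits (Protocol 6.2.2, 6.2.3), so the actual numbers will be lower. The inflation factors do not depend on the sample size.

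**5. Net gain against the model as planned**

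If the present covariates explain a share Rc², the SE of the planned model relative to the proposed one is √[(1 − Rc²)/(1 − R²)]. This is below the tabulated factor whenever Rc² exceeds zero. For FEV1/FVC, a ratio, R² is probably smaller too.

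**The case against.** The strongest defence is that the covariates are the subject of the analysis. SAP 10.1 says lung function is to be assessed in relation to them. No objective asks for an arm effect on lung function, the arm effects on asthma and sensitisation are tested elsewhere without such adjustment, and section 10 lies outside the numbered endpoints. This justifies keeping the model. It does not justify making it the only arm comparison, which is how 10.1.1 is written. For TEWL, SAP 8.4.4.1 compares the arms first without and then with adjustment for eczema and sensitisation.

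A reader might infer more than the documents support:

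- **That the comparison is biased as written.** This requires that the arm changes asthma, medication or sensitisation, which the documents leave open. In the scenarios above, the 0.025 to 0.050 SD lost is also well below the detectable difference under either model.
- **That omitting age, sex and height biases the result.** In randomised participants and a linear model, it does not in itself.
- **That a fixed precision gain is available.** R² is assumed, the outcome scale is not stated, and the present covariates may themselves be prognostic.
- **That ages will spread evenly from 9.5 to 16.5.** The upper end is a theoretical maximum; the plan describes participants as about 12.
- **That the covariates are post-randomisation in every sibling.** Siblings take their arm from the LEAP participant, and an older sibling's asthma or sensitisation may predate the intervention.

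One more objection stands: height at Visit 144 is also measured after randomisation, in a study that examines nutritional effects. The fix has to allow for that.

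**Conclusion.** The point holds, with modest weight. As written, the sole arm comparison of FEV1, FEV1/FVC and peak flow conditions on variables that, in LEAP participants, follow randomisation and are tested as outcomes of the arm. If the intervention changes them, the total effect on lung function is not estimated. How much is lost depends on how far the effect acts through them, which the documents cannot tell us.

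The omission of age, sex and height is a precision problem in randomised participants: SE inflation of about 1.1 to 2.2 times for an assumed R² of 0.2 to 0.8, for raw FEV1 or peak flow, against a model with no other covariates. The net loss is smaller if the present covariates are prognostic, and smaller for FEV1/FVC. If standardised values were intended, the precision point falls away, but the SAP must say so. Siblings have no age limit, so the omission matters at least as much there. The co-primary endpoints are not affected.

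**What to change.** Revise SAP 10.1 along the lines of its own TEWL plan:

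- **Main arm comparison.** Use a model with arm, age, sex and height, or age-sex-height standardised values, without the Visit 144 asthma symptom, medication and sensitisation covariates. Keep the random family effect for siblings. State whether each outcome is raw or standardised.
- **Secondary description.** Keep the present model, labelled as describing lung function in relation to those variables and not as the effect of the intervention.
- **Sensitivity model.** Because height is measured after randomisation, also report a model with age and sex only. Use that model for siblings aged 18 or over, for whom height is not required.

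The cost is SAP wording and a few more models in a low-priority section. No new data are needed: age and sex are summarised at Visit 144 (SAP 6.2), and spirometry takes place at the clinic, where height is scheduled for participants and for siblings under 18.

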10.1.2. LEAP Siblings

FEV1 measurements collected at V144 for the LEAP Siblings in the ITT population will be compared between LEAP Consumers and LEAP Avoiders using a linear mixed effects model with a random family effect included to account for the clustering of siblings within family units and the analysis of multiple siblings. Covariates for asthma symptoms, asthma medication use and aeroallergen sensitization will be added to the model. The distribution of FEV1 will be examined to determine if a transformation should be applied to the measurements. Older Siblings and Younger Siblings will be analyzed separately.

The same statistical methodology will be repeated to analyze FEV1/FVC and peak flow.

11. CHANGES TO THE ANALYSES PLANNED IN THE PROTOCOL

Section 9.1 of the protocol stated the following ITT sample definition for LEAP Participants: "any participant who enrolled in the LEAP Participant cohort who is evaluable for allergy." In section 5.1 of the SAP, the ITT sample for LEAP Participants was changed to: "Any participant who enrolled in the LEAP Trio Participant cohort for whom at least one Visit 144 assessment is available." This change to the ITT sample definition will allow secondary and exploratory analyses to include LEAP Participants whose peanut allergy status is not able to be determined due to missing assessments.

Section 9.1 of the protocol stated the following PP sample definition for the LEAP Parents: "There is no per-protocol sample for this cohort." In section 5.3 of the SAP, the PP sample for LEAP Parents was changed to: "Any participant in the ITT sample whose child was in the LEAP PP sample." This change to the PP sample definition will allow the inclusion of sensitivity, secondary and exploratory analyses for the LEAP Parents whose children were included in the LEAP Participant PP sample.

